### CLINICAL STUDY PROTOCOL SYNOPSIS

TITLE	A randomized controlled clinical trial assessing the efficacy of DEXTENZA, sustained release dexamethasone 0.4 mg insert, when placed within the lower eye eyelid canaliculus in comparison to topical prednisolone acetate following bilateral small incision lenticule extraction (SMILE).
SITE LOCATION(S)	Toledo LASIK & Cataract
PRINCIPAL INVESTIGATOR	[name]
OBJECTIVE(S)	Assessing DEXTENZA efficacy when placed within the lower eyelid canaliculus post SMILE in comparison to topical prednisolone acetate.
STUDY DESIGN	A randomized controlled clinical trial assessing the efficacy of DEXTENZA, sustained release dexamethasone 0.4 mg insert, when placed within the lower eye eyelid canaliculus in comparison to topical prednisolone acetate following bilateral small incision lenticule extraction (SMILE).
STUDY DURATION	3 months
ESTIMATED STUDY COMPLETION DATE	3 months
POPULATION	
Sample Size:	20
Target Population:	Patients undergoing bilateral SMILE
TREATMENT(S)	
Study Drug	Sustained Release Dexamethasone, 0.4 mg
Dose/Route/Schedule:	All patients will receive: First eye randomized for either topical prednisolone acetate (Control eye) or lower eyelid canaliculus DEXTENZA insertion (Study Eye) insertion and the contralateral eye receiving the opposite treatment in the OR following SMILE
ENDPOINT(S)	

**Primary:**

- Patient preference as measured by Patient Symptoms Questionnaire
- Mean change in pain score
  - Post op pain scores as measured on a scale from 0-10 (Days 1,7,30)
- Mean change in AC cell and flare score
  - Post op inflammation scores as measured on a scale of 0-4 (Days 1,7,30)
    - Absence of cell to be defined as a grade of: 0-0.5
    - Absence of flare to be defined as a grade of: 0-1

**Secondary:**

- Mean change BCVA
- Mean change in UCVA
- Proportion of patient call backs on post-operative management per eye (E.H.R. chart documentation)

---

TABLE OF CONTENTS

Clinical Study Protocol Synopsis.....	2
List of Tables.....	5
1. Introduction and Rationale.....	6
1.1    Introduction .....	6
1.2    Rationale .....	6
1.2.1    Rationale for Study Design .....	6
2. Study Objectives.....	6
2.1    Primary Objective.....	6
2.2    Secondary Objectives .....	6
3. Study Design.....	7
3.1    Study Description and Duration .....	7
4. Selection, Withdrawal, and Replacement of Patients .....	7
4.1    Study Population .....	7
4.1.1    Inclusion Criteria.....	7
4.1.2    Exclusion Criteria.....	7
4.2    Treatment Logistics and Accountability.....	7
4.2.1    Packaging, Labeling, and Storage.....	7
4.2.2    Supply and Disposition of Treatments .....	8
4.2.3    Treatment Accountability.....	8
4.3    Concomitant Medications and Procedures .....	8
5. Study Schedule of Events and Visit Descriptions.....	9
5.1    Schedule of Events .....	9
5.2    Study Visit Descriptions.....	11
5.2.1    Study Procedures .....	11
5.2.2    Unscheduled Visits .....	12
5.2.3    Adverse Event Information Collection .....	12
5.3    Rescue Criteria .....	12
6. Safety Definitions, Reporting, and Monitoring .....	12
6.1    Definitions .....	12
6.1.1    Adverse Event.....	12
6.1.2    Serious Adverse Event .....	13

6.2	Recording and Reporting Adverse Events.....	13
7.	Study Variables .....	14
7.1	Demographic and Baseline Characteristics .....	14
8.	Ethical and Regulatory Considerations.....	14
8.1	Good Clinical Practice Statement.....	14
8.2	Informed Consent .....	14
8.3	Patient Confidentiality and Data Protection .....	14
8.4	Institutional Review Board.....	15
LIST OF TABLES		
Table 1	Schedule of Events.....	10

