**2.2 Secondary Objectives**

To determine the effect of dexamethasone insert through Week 12 as measured by:

- Mean change BCVA
- Mean change in UCVA
- Proportion of patient call backs on post-operative management per eye (E.H.R. chart documentation)

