### **3. STUDY DESIGN**

#### **3.1 Study Description and Duration**

This three-month prospective, open-label, single-center, randomized investigator initiated clinical study seeks to investigate the efficacy of DEXTENZA when placed in the lower canaliculus (study eye) compared to topical corticosteroids (control eye) following bilateral SMILE surgery. In addition, the study will evaluate physician assessment of ease of DEXTENZA insertion

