### **4. SELECTION, WITHDRAWAL, AND REPLACEMENT OF PATIENTS**

#### **4.1 Study Population**

The study aims to enroll 20 patients undergoing bilateral SMILE.

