Prospective, Randomized, Fellow Eye-Controlled Study of Postoperative Pain and Inflammation Control with an Intracanalicular Dexamethasone 0.4 mg Ophthalmic Insert Following Small Incision Lenticule Extraction

22NOVEMBER2022

NCT04380857

Statistical Analysis Plan:

No formal power analysis was conducted, and the sample size was set at 40 eyes based on the sample size used in several similar prior studies.^{18–20} Chi-square tests were used to compare proportions and t-tests to compare means. The level of significance was set at 0.05.

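### The call-back endpoint has no defined unit and no rule for assigning a call to an eye, and the unpaired chi-square test does not suit it whichever unit is chosen

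*Protocol*

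**What the plan says.** The endpoint appears twice in the protocol, in the synopsis and in section 2.2, in the same words: "Proportion of patient call backs on post-operative management per eye (E.H.R. chart documentation". Section 2.2 gives the window: "To determine the effect of dexamethasone insert through Week 12 as measured by". Nothing states the numerator, the denominator, how repeat calls are handled, or what happens to a call about both eyes or neither. Call backs have no row in Table 1 and no entry in the visit lists of section 5.2.1, so the chart is the only named source.

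Each patient has one eye on each treatment, with "the contralateral eye receiving the opposite treatment in the OR following SMILE". Section 3.1 describes "This three-month prospective, open-label, single-center, randomized investigator initiated clinical study", so patient and staff know which eye had the insert.

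The SAP does not mention this endpoint. Its general rule is "Chi-square tests were used to compare proportions and t-tests to compare means", and "The level of significance was set at 0.05". It names no paired, clustered or exact method.

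**The concern.** A call is made by a patient, but the endpoint is reported by eye. Someone must decide which eye the call was about. No rule guides that decision, and the people who write and read the chart are not masked.

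The phrase can be read in three ways: each eye group's share of all calls, calls divided by eyes, or the proportion of eyes with at least one call. Under the first two, several calls from one patient enter a chi-square test as independent observations. Under the third, repeat calls do no harm, but the two eyes of a patient are analysed as if they came from different people.

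The same charts can therefore give different answers according to a choice made after the data are seen. A difference in post-operative calls could be reported as significant when it reflects one anxious patient, or the way ambiguous calls were allocated.

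**Working it through.** **Inputs from the documents.** 20 patients (protocol section 4.1: "The study aims to enroll 20 patients undergoing bilateral SMILE"); 40 eyes (SAP: "No formal power analysis was conducted, and the sample size was set at 40 eyes"); significance level 0.05, taken as two-sided because the SAP does not say. The plan's one design figure reproduces: 20 × 2 = 40 eyes, 20 per treatment. There is no power calculation or call rate to reproduce.

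**1. Calls as the unit, tested against a 50:50 split.** With A and B calls charted to the two eye groups, chi-square = (A − B)²/(A + B) on 1 df.
- One patient makes the only calls, all to one eye. Three calls: 9/3 = 3.0, p = 0.083. Four calls: 16/4 = 4.0, p = 0.0455. An exact binomial test would need six calls (p = 0.031).
- With balanced calls from other patients, one caller must add more: 6 calls on 1 v 1 (7 v 1: 36/8 = 4.50, p = 0.034); 8 on 3 v 3 (11 v 3: 64/14 = 4.57, p = 0.033); 9 on 5 v 5 (14 v 5: 81/19 = 4.26, p = 0.039).
- Constructed example: 10 v 2 calls gives 64/12 = 5.33, p = 0.021. If 8 of the 10 come from one patient and every other call from a different patient, the eyes with a call number 3 v 2, exact p = 1.0.

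**2. Calls divided by 20 eyes, 2×2 chi-square.** 0/20 v 4/20: 0.2²/(0.1 × 0.9 × 0.1) = 4.44, p = 0.035 uncorrected. With Yates' correction, 0/20 v 6/20 is needed (p = 0.027).

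**3. Eyes with at least one call.** A patient who calls about one eye moves the comparison by one eye, however often they call. A one-eye difference gives uncorrected p = 0.31 (0 v 1 of 20) to 0.75 (9 v 10 of 20).

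**4. Type I error under assumed call rates.** 100,000 simulated trials per cell, 20 patients, no treatment effect. Calls per patient are gamma-Poisson with shape 0.5 or 5; ranges run over the shapes and means in each row. Simulation standard error is at most 0.16 percentage points.

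| Mean calls per patient | How calls fall to eyes | Chi-square on calls | Unpaired chi-square on eyes | Exact McNemar on eyes |
|---|---|---|---|---|
| 0.6 to 1.0 | All of a patient's calls to one eye | 12.4% to 32.3% | 7.1% to 11.0% | 1.5% to 2.4% |
| 0.6 to 1.0 | Eye share uniform across patients | 7.0% to 15.7% | 2.9% to 6.2% | 1.0% to 2.2% |
| 0.6 to 1.0 | Each call to either eye at random | 4.5% to 5.2% | 1.6% to 4.6% | 0.8% to 2.1% |
| 0.25 | All three patterns | 4.1% to 11.5% | 2.4% to 5.6% | 0.2% to 0.6% |

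**5. Reach of the exact McNemar test.** With d discordant patients all in one direction, p = 2 × 0.5^d: d = 5 gives 0.0625, d = 6 gives 0.031.

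**The case against.** A reader might infer that the endpoint counts calls and not eyes, so that its false-positive rate is well above 5%. The documents do not support that as a flat statement. The noun is call backs, but it is qualified as per eye and the sample size is given in eyes, so the proportion of eyes with a call is an equally natural reading. On that reading one frequent caller cannot produce significance.

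Even if calls are counted, inflation needs repeat calls that cluster on one eye within a patient. If each call falls to either eye at random there is none. The documents give no call rate and no evidence on whether repeat calls concern the same eye. The 50:50 test is also one choice of chi-square, since the SAP does not say which table it would use. The 10 v 2 example shows what is possible, not what is likely.

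A reader might also infer that the insert's convenience claim rests on this endpoint. It does not: patient preference is a primary endpoint, and call backs are the last of three secondary ones.

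All of this stands and limits the size of the point. It does not supply a unit or an attribution rule, and it does not make an unpaired test right for fellow eyes.

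**Conclusion.** The point holds in conditional form. The unit of the endpoint and the assignment of calls to eyes are undefined, and that is so on every reading. The only test offered is wrong for repeat calls if calls are counted, and ignores the pairing if eyes are counted.

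If calls are counted, the type I error depends mainly on clustering by eye within patient: up to about 32% at the assumed rates of 0.6 to 1.0 calls per patient, and close to nominal without clustering. If eyes are counted, the unpaired test runs from about 2% to 11% in the same scenarios, so it can err in either direction. These percentages illustrate assumed call rates and are not estimates for this trial.

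This is a secondary endpoint in a trial of 20 patients. The change should be made, but the primary endpoints are unaffected.

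**What to change.** - Define the endpoint as at least one call back attributed to that eye (yes/no) through Week 12, the single window that section 2.2 already sets.
- Record the eye when the call is taken: insert eye, drop eye, or both/unclear. The SAP is written in the past tense, so calls may already have been collected. In that case, write down the attribution rule before the analysis.
- Compare eyes within patient by the exact McNemar test on the 20 pairs.
- Report the number of calls, and the both/unclear calls, descriptively. Do not allocate the latter to an eye.

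The work is one field on the call log, or a written chart-reading rule, and a sentence or two in the SAP. The statistical cost is real. Repeat calls no longer add to the test. Exact McNemar is conservative here (type I error about 2% or less) and cannot reach p < 0.05 with fewer than six discordant patients, even if all favour the same treatment. If few patients call, the result will be descriptive in practice, and the SAP should say so.

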**1. INTRODUCTION AND RATIONALE**

**1.1 Introduction**

Drug delivery platforms are an innovative exciting advancement in ophthalmology. They allow patients to eliminate topical medications which are generally associated with lack of compliance, difficulty of use and requiring help from family members. These delivery systems can be applied easily during refractive surgeries, and patients do not have to worry about drop insertion in their post-operative regimen.

**1.2 Rationale**

Following SMILE surgery, the current standard of care is to prescribe corticosteroid drops to treat both ocular pain and inflammation. Typically, a tapering dose of topical corticosteroids is prescribed and tapered throughout the post-operative period, generally 2 weeks. Patients are expected to administer multiple drops throughout the days and weeks following surgery. There are limitations with the standard of care, these include; patient noncompliance, difficulty in administration and poor accuracy of drops getting into the eye.

**1.2.1 Rationale for Study Design**

This study will compare and evaluate the benefit of treatment with a physician administered intracanalicular dexamethasone insert, in the lower canaliculus (study eye) compared to topical corticosteroids (control eye) following bilateral SMILE surgery. In addition, the study will evaluate physician assessment of ease of DEXTENZA insertion

**2. STUDY OBJECTIVES**

**2.1 Primary Objective**

To determine the effect of dexamethasone insert through Week 12 as measured by:

- Patient preference
- Mean change in pain score
  - Post op pain scores as measured on a scale from 0-10 (Days 1,7,30)
- Mean change in AC cell and flare score
  - Post op inflammation scores as measured on a scale of 0-4 (Days 1,7,30)
    - Absence of cell to be defined as a grade of: 0-0.5
    - Absence of flare to be defined as a grade of: 0-1

**2.2 Secondary Objectives**

To determine the effect of dexamethasone insert through Week 12 as measured by:

- Mean change BCVA
- Mean change in UCVA
- Proportion of patient call backs on post-operative management per eye (E.H.R. chart documentation)

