**[name] STUDY**

**Table 1 Schedule of Events**

Study Procedure	Screening/ Baseline	Surgical Visit Day 0	Day 1	Day 7	Day 30	3 MTH post-op	Early Termin- ation
Visit	VISIT 1	VISIT 2	VISIT 3	VISIT 4	VISIT 5	VISIT 6	
Windows for Visits	(Day -30 to -1)			+/- 3 day	+/- 5 days	+/- 7 days	
Inclusion/Exclusion	x						
Informed Consent	x						
Demographics	x						
Medical History and Concurrent Illnesses	x						
Concomitant Medications	x	x	x	x	x	x	
Distance UCVA testing	x		x	x	x	x	
BCVA (ETDRS at 4m)	x			x	x	x	
Ophthalmic Examination (w or w/o dilated fundus exam)	x	x	x	x	x	x	
Pentacam	x						
Intraocular Pressure	x			x	x	x	
Indicate the incision type, location, and size (mm)			x	x	x	x	
Record any surgical complications	x	x	x	x	x	x	
Subject reported AEs prior to or after surgery	x	x	x	x	x	x	
Intracanalicular dexamethasone insert*		x					
Patient Treatment Preference			x	x	x	x	
Ocular Pain Assessment	x		x	x	x	x	
Anterior chamber cell count	x		x	x	x	x	
Anterior chamber cell flare	x		x	x	x	x	
Insert Visualization		x	x	x	x	x	

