## **5.2 Study Visit Descriptions**

### **5.2.1 Study Procedures**

#### **Screening/Baseline**

- Inclusion/Exclusion Criteria
- Informed consent
- Demographics
- Medical history and concurrent illnesses
- Concomitant medications
- Ocular Pain Assessment Scale
- Distance UCVA (OD, OS, OU)
- Best-corrected visual acuity as measured by ETDRS chart at 4m
- Intraocular Pressure
- Ophthalmic Examination (including dilated fundus exam)
  - anterior chamber cell count
  - anterior chamber cell flare
- Pentacam
- IOP
- Subject reported AE's prior to or after surgery

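### If the UCVA outcome is change from screening, the SAP's unadjusted t-test may give up precision, and close matching of fellow eyes prevents that only if the test is paired

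*Protocol*

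**What the plan says.** Protocol section 2.2 and the synopsis list "Mean change in UCVA" among the secondary measures, followed through Week 12. Neither gives the time from which change is measured, the visit that counts, or the acuity scale.

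UCVA is taken in each eye at screening (section 5.2.1: "Distance UCVA (OD, OS, OU"). The Table 1 row "Distance UCVA testing" adds Day 1, Day 7, Day 30 and 3 months. Screening is the only pre-operative measurement.

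The design is within patient. One eye is randomised to the insert or drops, with "the contralateral eye receiving the opposite treatment in the OR following SMILE" (synopsis). Section 4.1 gives the size: "The study aims to enroll 20 patients undergoing bilateral SMILE". The SAP counts this as 40 eyes and reports no formal power analysis. Its whole method is "Chi-square tests were used to compare proportions and t-tests to compare means", at a 0.05 level. It mentions neither pairing nor a covariate.

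**The concern.** SMILE is meant to correct the refractive error that drives uncorrected acuity before surgery. An eye's screening UCVA may therefore say little about its post-operative UCVA. If so, subtracting the screening value removes little noise from the outcome and adds the whole screening difference between the two eyes.

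The eligibility criteria set no limit on how far a patient's eyes may differ before surgery, so close matching cannot be taken for granted. With only 20 pairs, the treatment difference in UCVA could be reported with a wider interval than the collected data allow. The SAP's silence on pairing adds a second route to the same loss.

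**Working it through.** **The plan's own figure.** There is no power calculation to reproduce. Only the count can be checked: 20 patients × 2 eyes = 40 eyes, which agrees.

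**Inputs.** From the documents: n = 20 pairs and a 0.05 level (taken as two-sided). Everything else is assumed, because the documents give no UCVA SD, scale or correlation:
- The SD of the post-operative between-eye difference is set to 1, and that of the screening difference to k.
- r is the correlation of the two differences. It is probably low for refractive surgery; 0 to 0.3 is used, with 0.5 as a check.
- The true difference is 0.66 SD, chosen because it gives a paired t-test on post-operative UCVA 80% power.
- Data are normal.

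**Paired analyses.**
- Change from screening: SD = √(1 + k² − 2rk). This exceeds 1, so subtracting does harm compared with using post-operative UCVA alone, whenever k > 2r.
- Adjusted (post-operative difference regressed on screening difference, intercept reported): residual SD = √(1 − r²). The standard error carries a further factor √((n−2)/(n−3)) = √(18/17) = 1.03 for the covariate. Relative to the plain paired test this gives 1.03 at r = 0 and √0.91 × 1.03 = 0.98 at r = 0.3.

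Example, k = 1 and r = 0: SD(change) = √2 = 1.41, so the interval is about 1.41 times as wide as that from post-operative UCVA alone.

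| k | SD(change), r = 0 / 0.3 | Power on change, r = 0 / 0.3 / 0.5 | Power adjusted, r = 0 / 0.3 / 0.5 |
|---|---|---|---|
| 0.25 | 1.03 / 0.96 | 78 / 83 / 87% | 78 / 81 / 88% |
| 0.5 | 1.12 / 0.97 | 71 / 82 / 90% | 78 / 81 / 88% |
| 1 | 1.41 / 1.18 | 51 / 66 / 80% | 78 / 81 / 88% |
| 2 | 2.24 / 1.95 | 24 / 30 / 37% | 78 / 81 / 88% |

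Power on change agrees between the noncentral t distribution and simulation; power for the regression is simulated. Simulated type I error is 0.048–0.052 for both methods in every cell, so the paired test on change is valid and only less precise in some cells.

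**Two-sample test on 40 eyes.** Take the favourable cell k = 0.25, r = 0, and assume inter-eye correlations of 0.95 at screening and 0.5 after surgery.
- Post-operative variance per eye: 1 = 2σ²(1 − 0.5), so σ² = 1.
- Screening variance per eye: 0.0625 = 2σ²(1 − 0.95), so σ² = 0.625.
- Two-sample SE = √(2 × 1.625/20) = 0.403.
- Paired SE = √(1.0625/20) = 0.230.

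The ratio is 1.75, and power is about 28% against 78% for the paired test. With screening correlation 0.99 and the same k, the screening variance is 3.125, the two-sample SE is √(2 × 4.125/20) = 0.642, and power is about 2%. With complete pairs the point estimate is the same for both tests. The loss lies in a standard error that still contains between-patient screening variation, and type I error falls close to zero instead of 0.05.

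**The case against.** The strongest objection is that nothing in the documents fixes the size. The benchmark effect, k and r are all assumed, and within the range the change score sometimes does better: 82% against 79% at k = 0.25, r = 0.2, and 90% against 88% at k = 0.5, r = 0.5. This stands. The loss is possible but not demonstrated, and as no power was planned, none that was promised is lost.

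A paired t-test on change is also valid and unbiased, since treatment is randomised between fellow eyes, and no primary conclusion depends on UCVA. This stands too, and keeps the priority low.

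Change from screening might not be intended. The primary outcomes also use mean change but describe post-operative scores: "Post op pain scores as measured on a scale from 0-10 (Days 1,7,30" and "Post op inflammation scores as measured on a scale of 0-4 (Days 1,7,30". A reader might infer that nothing is subtracted there, and so nothing for UCVA. The documents do not establish this, because pain, cell and flare are also recorded at screening. The reference time is open for all of these outcomes.

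A reader might also infer that well-matched eyes make the planned test safe. That is true only of a paired test. The SAP does not say its test is paired, and with a two-sample test matching does not remove the loss.

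**Conclusion.** The point holds as a conditional. If change is from screening, an unadjusted t-test may lose precision:
- **Paired test:** no material loss at k of about 0.25; a loss of 15 to 27 power points at k = 1 (51–66% against 78–81%), and more at k = 2, for r of 0 to 0.3.
- **Two-sample test:** a loss remains however closely fellow eyes match.

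The sizes rest on assumed k, r, inter-eye correlations and effect, with normal data. The documents do not support a claim of bias, nor a claim that precision will certainly be lost. The endpoint is secondary, so this is a cheap optional improvement, held with medium confidence.

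**What to change.** In the SAP:
1. State that insert and drop eyes are compared within patient.
2. Define the outcome as post-operative UCVA on a stated scale, for example logMAR.
3. Name one main visit. Follow-up through Week 12 points to the 3-month visit; treat Day 1, Day 7 and Day 30 as supportive.
4. Regress the insert-minus-drop difference in post-operative UCVA on the same difference in screening UCVA, and report the intercept with its 95% confidence interval.

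A plain paired t-test on post-operative UCVA is an acceptable simpler choice. When r is low it gives most of the gain, because the gain comes from not subtracting the screening value. The covariate mainly helps if r is higher.

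**Cost.** SAP wording and one degree of freedom; no new data. Against the plain paired t-test, the covariate loses about 2 power points at r = 0 (78% v 80%), and gains about 1 at r = 0.3 and 8 at r = 0.5. Against a paired t-test on change, it can be about 2 points worse if eyes are closely matched.

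The SAP is dated November 2022 and written in the past tense. If outcome data have been seen, label this analysis post hoc and show it beside the planned one.
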